10.4. Safety

Safety will be analyzed principally by examination of the frequency of adverse events. In particular, the number of heart graft-related serious adverse events (HGRSAEs) up to the 30-day follow-up after transplantation per subject will be analyzed. This endpoint is defined to consist of the following adverse events (at most one per type), if they are serious adverse events:

- Moderate or severe primary heart graft dysfunction (PGD) (left or right ventricle) (not including rejection or cardiac tamponade) according to ISHLT consensus manuscript.
- Primary graft failure requiring re-transplantation.

This endpoint will be summarized using descriptive statistics, specifically the mean, median, standard deviation, minimum, maximum, and a 95% confidence interval for the mean based on the t-distribution.

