Secondary Endpoints	
 Patient and graft survival at Day-30 post-transplant Incidence of severe primary heart graft dysfunction (PGD) (LV or RV) in the first 24 hours post-transplantation according to ISHLT consensus manuscript (as defined in Appendix 1 of the protocol) Rate of donor heart utilization, defined as the proportion of eligible donor hearts that were successfully transplanted after preservation and assessment on the OCS Heart System.
Other Endpoints	
 Patient survival at 6 and 12 months post-transplant Incidence of primary graft failure requiring re-transplantation through 12 months post-transplant Duration of initial post-transplant ICU stay Duration of initial post-transplant hospital stay.
Safety	
Incidence of heart graft-related Serious Adverse Events (HGRSAEs) in the first 30 days post heart transplantation, defined as:
 
 Moderate or Severe primary heart graft dysfunction (PGD) (left or right ventricle) (not including rejection or cardiac tamponade) according to ISHLT consensus manuscript (as defined in Appendix 1 of the protocol). Primary graft failure requiring re-transplantation.
Follow-up	All patients will be followed for 12 months post-transplant (including post-market).

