Statistical Methods	
The transplanted recipient population will consist of all recipients who are transplanted according to this protocol. The analyses of all effectiveness and safety endpoints, except the rate of donor heart utilization, will be based on the transplanted recipient population.
 
The OCS heart population will consist of all donor hearts that are instrumented on the OCS Heart System. The analysis of the rate of donor heart utilization that were successfully transplanted after preservation and assessment on the OCS Heart System will be based on the OCS heart population.
 
The primary endpoint will be summarized using counts and percentages and an exact 95% confidence interval for the true percentage based on the binomial distribution.
 
Each secondary effectiveness endpoint will be summarized using counts and percentages and an exact 95% confidence interval for the true percentage based on the binomial distribution. The first two secondary effectiveness endpoints will be analyzed using the transplanted recipient population.
 
The rate of donor hearts that were successfully transplanted after preservation and assessment on the OCS Heart System (i.e., donor heart utilization), will be analyzed using the OCS heart population.
 
Safety will be analyzed principally by examination of the frequency of adverse events. In particular, the number of heart graft-related serious adverse events (HGRSAEs) up to the 30-day follow-up after transplantation per subject will be analyzed. This endpoint is defined to consist of the following adverse events (at most one per type), if they are serious adverse events:
 
 Moderate or severe primary heart graft dysfunction (PGD) (left or right ventricle) (not including rejection or cardiac tamponade) according to ISHLT consensus manuscript (as defined in Appendix 1 of the protocol). Primary graft failure requiring re-transplantation.

[figure not shown]
	This endpoint will be summarized using descriptive statistics, specifically the mean, median, standard deviation, minimum, maximum, and a 95% confidence interval for the mean based on the t-distribution.
Determination of Sample Size	This is a continued access protocol and does not have a statistically determined sample size
Trial Sponsor	TransMedics, Inc. [name]

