2.2.1. Donor Heart Utilization

The Heart EXPAND trial was designed for 75 subjects at 20 US sites. The primary effectiveness endpoint is a composite of patient survival at Day 30 post-transplant and freedom from severe primary graft dysfunction (PGD) at 24 hours post-transplant. Secondary endpoints include: donor heart utilization rate (i.e., how many of these non-standard hearts were actually transplanted after OCS Heart System preservation and assessment), 30-day survival and freedom from severe PGD at 24 hours after transplant. The primary hypothesis for this trial is that the true proportion of transplanted recipients with the composite of patient survival at Day 30 post-transplantation and freedom from severe PGD in the first 24 hours post-transplantation is greater than the Performance Goal value of 0.65 (65%). This performance goal is based on literature and statistics for standard criteria heart transplants. Prior to the Heart EXPAND trial, there were no data available on post-transplant outcomes of extended criteria donor hearts.

The safety endpoint is the number of heart graft-related serious adverse events (HGRSAEs) up to the 30-day follow-up after transplantation per subject. The endpoint is defined to consist of the following adverse events (at most one per type) if they are serious adverse events:

- Moderate or severe primary heart graft dysfunction (PGD) (left or right ventricle) (not including rejection or cardiac tamponade) as defined in Appendix 2 of the protocol, according to the ISHLT consensus manuscript.
- Primary graft failure requiring re-transplantation

The Heart EXPAND trial is a single arm study of extended criteria donor hearts, i.e., those that are currently not transplanted or are seldom transplanted in the US. To be included in this study, donor hearts had to have met one or more of the following inclusion criteria:

- Expected total cross-clamp time of ≥ 4 hours
- Expected total cross-clamp time of ≥ 2 hours **PLUS** one or more of the following risk factors:
 - Donor age 45-55 years old with no coronary catheterization data, or
 - Donor age ≥ 55 years old; or
 - Left ventricular septal or posterior wall thickness of $>12 \leq 16$ mm; or
 - Reported down time of ≥ 20 min, with stable hemodynamics at time of final assessment; or
 - Left heart ejection fraction (EF) $\geq 40 \leq 50\%$; or
 - Donor angiogram with luminal irregularities with no significant CAD

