2.2.6. Heart EXPAND Trial Results – Patient Survival

All subjects have reached the primary endpoint time point of 30-days and the follow-up timepoint of 6 months. Follow-up at 12 months is still on-going. Survival is shown in Table 4 below. At 30 days post-transplant, survival was 94.7% and at 6 months, survival was 88%.

Table 4: Summary of available survival data for subjects in OCS Heart EXPAND trial

	Survival OCS Heart EXPAND N=75
30 days (% n/N)	94.7% (71/75)
Hospital Discharge (% n/N)	92.0% (69/75)
6 months (% n/N)	88.0% (66/75)

As of the date of this report, 12-month follow-up is available for 40 of the 75 enrolled subjects. Two additional patients died between 6 and 12 months.

2.2.7. Heart EXPAND Trial Results – Primary Graft Dysfunction (PGD) and Heart Graft-Related Serious Adverse Events (HGRSAEs)

The second component of the primary endpoint, severe Primary Graft Dysfunction (PGD) at 24 hours, is shown in [Table 5](#) below. There was a 10.7% (8/75) incidence of severe PGD following transplant for the Heart EXPAND subjects.

Table 5: Severe PGD in the first 24 Hours for Heart EXPAND Subjects

Adjudicated Primary Graft Dysfunction	OCS Heart EXPAND N=75
Severe PGD	10.7% (8/75)
PGD-LV with implantation of ECMO	8.0% (6/75)
PGD-RV with implantation of RVAD	2.7% (2/75)

The incidence of moderate or severe PGD within 30 days of follow-up was 12.0% (9/75). One patient (1.3%) had primary graft failure requiring re-transplantation.

Both the incidence of severe PGD within 24 hours and the incidence of moderate and severe PGD within 30 days after transplant observed in the Heart EXPAND trial were comparable to, or in some cases, substantially less than the values reported in the literature, which ranged from 13% to 36% (Dronavalli, et al., 2013; D'Alessandro et al., 2011; Lima et al., 2006), including more recent studies which utilized the ISHLT criteria (Nicoara, et al. 2018; Singh et al., 2018; Sabatino et al., 2017; Squiers, et al., 2017).

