5.3. Safety

The safety endpoint is defined as the incidence of heart graft-related Serious Adverse Events (HGRSAEs) in the first 30 days post heart transplantation, defined as:

- Moderate or Severe primary heart graft dysfunction (PGD) (left or right ventricle) (not including rejection or cardiac tamponade) according to ISHLT consensus manuscript.
- Primary graft failure requiring re-transplantation.

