9.5.2. Severity

The investigator will rate the severity of the serious adverse event using the following categories:

- **Mild:** The adverse event is transient and/or easily tolerated by the subject.
- **Moderate:** The adverse event causes the subject discomfort and interrupts the subject's usual activities.
- **Severe:** The adverse event causes considerable interference with the subject's usual activities.

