10.4.1. Other Safety Analyses

In addition, the numbers and percentages of subjects experiencing at least one (definitely or probably-related) serious device-related AE, at least one unanticipated SAE, and the number and percentage of deaths will all be tabulated. SAEs will also be tabulated using counts and percentages alone and in regards to the relationship of the SAE to the device, and the severity of the SAE.

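### The 30-day safety endpoint is defined as an incidence but summarised as a mean count with a t-interval; the percentage of recipients affected gets no row and no confidence interval

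*Combined protocol and SAP*

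**What the plan says.** Section 5.3 states: "The safety endpoint is defined as the incidence of heart graft-related Serious Adverse Events (HGRSAEs) in the first 30 days post heart transplantation". The Safety row of the synopsis uses the same term: "Incidence of heart graft-related Serious Adverse Events (HGRSAEs) in the first 30 days post heart transplantation". Two event types qualify: moderate or severe primary graft dysfunction (PGD) by ISHLT grade, and primary graft failure leading to re-transplantation.

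Section 10.4 analyses the number of such events per recipient, counting each type at most once and only if serious. It reports "mean, median, standard deviation, minimum, maximum, and a 95% confidence interval for the mean based on the t-distribution". The synopsis (Statistical Methods) likewise plans "a 95% confidence interval for the mean based on the t-distribution".

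Section 10.4.1 lists at-least-one rows for device-related serious events and for unanticipated SAEs, together with deaths. HGRSAEs are not on that list. It adds that "SAEs will also be tabulated using counts and percentages alone", and also by device relationship and severity, without intervals. Severity there is the general scale of section 9.5.2 ("The investigator will rate the severity of the serious adverse event using the following categories": mild, moderate, severe).

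Sections 10.3.1 to 10.3.3 give exact binomial 95% intervals to the primary, secondary and other endpoints.

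**The concern.** The quantity named in the definition and the quantity analysed are different. An incidence is naturally read as the share of recipients with at least one event, and section 2.2.7 uses the word that way when it reports the parent trial as 9/75 and 1/75. The planned output is a mean count. The same mean can correspond to different numbers of affected recipients, so it does not show the incidence without further algebra.

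The only interval attached to this endpoint is also a normal-theory one for a sparse, skewed variable that takes three values. With such data the upper limit tends to be too low, which is the wrong direction for a safety rate. At stake is how clearly and accurately the named safety result is reported beside the parent trial's figures.

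**Working it through.** **Inputs.** n = 75 transplanted recipients (section 4.2). Parent-trial rates: moderate or severe PGD within 30 days 9/75, re-transplantation 1/75 (section 2.2.7). Both reproduce: 9/75 = 12.0% and 1/75 = 1.3%. The plan states no expected HGRSAE rate of its own.

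**Assumptions.** Section 2.2.7 does not say whether the re-transplanted recipient was among the nine with PGD, or whether re-transplantation fell within 30 days. I assume it did fall within 30 days, count all ten events as serious, and show both overlap patterns.

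**Step 1: planned summary against the incidence.** Let a recipients have one event and b have both. The sum is S = a + 2b and the sum of squares is Q = a + 4b. Then mean = S/75, SD² = (Q − S²/75)/74, and the t-interval is mean ± 1.9925 × SD/√75.

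| 10 events | S | Q | Mean | SD | t-interval for mean | Affected | Exact 95% CI |
|---|---|---|---|---|---|---|---|
| No overlap (a=10, b=0) | 10 | 10 | 0.133 | 0.342 | 0.055 to 0.212 | 10/75 = 13.3% | 6.6% to 23.2% |
| One recipient with both (a=8, b=1) | 10 | 12 | 0.133 | 0.380 | 0.046 to 0.221 | 9/75 = 12.0% | 5.6% to 21.6% |

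The mean is identical in the two rows while the incidence differs. In the second row the t upper limit is above the exact one. The two intervals there have different targets (mean count and proportion affected), so that comparison is loose.

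**Step 2: can the incidence be recovered?** Yes. Affected = a + b = (3S − Q)/2, which gives (30 − 10)/2 = 10 and (30 − 12)/2 = 9. Over 156 combinations (0 to 25 single-event and 0 to 5 double-event recipients), the affected count was recovered every time from the mean and SD rounded to two decimals.

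**Step 3: behaviour of the intervals at n = 75.** Exact enumeration, binomial or trinomial, with each interval scored against its own target (t: mean count; exact: proportion affected). An upper miss means the upper limit lies below the true value; nominal is 2.5%.

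| Scenario | t coverage | t upper miss | Exact coverage | Exact upper miss |
|---|---|---|---|---|
| PGD alone, 12% | 94.8% | 4.5% | 96.9% | 1.6% |
| 13.3%, no overlap | 93.7% | 5.4% | 96.0% | 2.2% |
| PGD 12%, re-transplantation 1/75, independent | 93.5% | 5.6% | about 96.0% | 2.4% |
| Same rates, re-transplantation only among PGD cases | 92.8% | 6.5% | 96.9% | 1.6% |
| Assumed 5%, single events | 89.0% | 10.6% | 96.6% | 2.1% |

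The 5% row is a sensitivity case that the documents do not supply.

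**Step 4: low counts.** Zero events give a t-interval of 0 to 0 (exact 0% to 4.8%). One event gives −0.013 to 0.040 (exact 0.03% to 7.2%).

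**Step 5: does another section fill the gap?** The SAE table in 10.4.1 may show PGD and re-transplantation by type, but it has no composite row and no interval. Its planned severity split follows 9.5.2, which rates discomfort and interference with activities. An HGRSAE is defined by ISHLT grade.

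**The case against.** The strongest reply is that most of the content already has an exact interval elsewhere. Section 10.3.2 covers severe PGD in the first 24 hours, and section 10.3.3 covers re-transplantation through 12 months. In the parent trial severe PGD was 8/75 (exact CI 4.7% to 19.9%) and moderate or severe PGD was 9/75 (5.6% to 21.6%), so the counts differ by one recipient. That is a fair limit on the weight of the point. These endpoints are still not the 30-day composite: one omits moderate PGD and the other uses a longer window.

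Second, the count is a legitimate carry-over. Section 2.2.1 says of the parent trial: "The safety endpoint is the number of heart graft-related serious adverse events (HGRSAEs) up to the 30-day follow-up after transplantation per subject". Section 10.4 is explicit about what it analyses, so the word incidence in 5.3 may simply be loose. This supports keeping the mean count, but it does not supply the percentage that 5.3 names.

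Third, the numerical effect is modest at parent-trial rates, and the exact upper limit is not always the higher one, as the overlap row in Step 1 shows. The marked failure of the t-interval needs a lower event rate than the parent trial saw. This stands.

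Fourth, nothing depends on the interval. The sample size is not statistical (section 10.5), the stopping rule in 15.8 uses 30-day deaths, and this endpoint has no test or performance goal. This also stands, and it is why the point is minor. In a descriptive protocol, though, estimates and intervals are the statistical output, so the named safety endpoint should appear as defined.

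**Conclusion.** The concern holds, as a minor reporting point. The safety endpoint is defined as an incidence and summarised as a mean count. The percentage of recipients affected has no direct row, and the one interval planned for the endpoint is moderately miscalibrated: coverage is 92.8% to 94.8% at parent-trial rates, with upper misses about two to two and a half times nominal (4.5/2.5 = 1.8; 6.5/2.5 = 2.6). The point estimate is not lost, because it follows from the mean, the SD and n. The figures rest on n = 75 and parent-trial rates, on that trial's re-transplantation having fallen within 30 days, on all events being serious, and on the overlap patterns shown.

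**What to change.** In section 10.4 and the synopsis, add the number and percentage of transplanted recipients with at least one HGRSAE within 30 days, with the exact binomial 95% interval already used in 10.3.1 and 10.3.2. Add the same three figures for each type within 30 days: moderate or severe PGD by ISHLT grade, and re-transplantation. At the parent trial's counts the by-type rows would read 9/75 = 12.0% (5.6% to 21.6%) and 1/75 = 1.3% (0.03% to 7.2%), so the new results could be set directly beside them. Keep the mean count as a supplementary description for continuity with the parent trial; dropping its t-interval is optional.

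The cost is a change of wording and a few table rows, with no new data. The displayed upper limit becomes slightly less favourable when no recipient has both events (10/75: 23.2% instead of 21.2%; 9/75: 21.6% instead of 19.5%). It can be slightly lower when one does (21.6% against 0.221 events per recipient).

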10.4.1. Other Safety Analyses

In addition, the numbers and percentages of subjects experiencing at least one (definitely or probably-related) serious device-related AE, at least one unanticipated SAE, and the number and percentage of deaths will all be tabulated. SAEs will also be tabulated using counts and percentages alone and in regards to the relationship of the SAE to the device, and the severity of the SAE.

10.5. Sample Size Determination

This is a continued access protocol and the sample size was not determined using statistical methods.

11. RISK ANALYSIS

This clinical trial has been designed to ensure that the benefits and knowledge gained from the trial outweigh the potential risks to the subjects.

11.1. Potential Risks

The potential risks to subjects from participation in this clinical trial include the following:

- **Potential Risks Associated with Heart Transplant Procedures:** These risks include post-operative complications not associated with the OCS™ Heart device such as graft failure, primary graft dysfunction, rejection, infection and other organs/systems complications, graft vessel disease (an expression of chronic rejection), infection, abnormal kidney function, diabetes, high level of cholesterol, high blood pressure, cancer and neurological complications.
- **The Potential Risks Associated with OCS Heart System:** Subjects have the risk of not receiving organs preserved with the OCS Heart System under certain conditions including: (1) the OCS Heart System may not work properly, or there may not be personnel available trained in the use of the Heart System or (2) the OCS Heart System may malfunction, or the medical staff may make an error which could lead to damage of the donor heart. If this occurs, the subject will have to wait for a new donor heart to become available. As with any medical device, there is always a risk of extremely rare or previously unknown side effects developing from the treatment.
- **Potential Risk of Using a Donor Heart that is Unsuitable for Transplantation:** Regardless of the preservation system that is used, there is the risk that a patient can receive a heart that does not adequately function. This trial is designed to utilize hearts that would not be accepted for transplantation using cold storage preservation. There is the possibility that using such hearts may increase the risk of transplanting a heart that does not function appropriately. It is also possible that the donor heart may not meet transplantability criteria after OCS preservation and would be turned down for transplant. In the EXPAND trial, only 19.4% of the donor hearts were turned down following OCS preservation so the anticipated frequency of this event is low.

11.2. Manner in Which the Potential Risks Have Been Minimized

The Sponsor has relied upon a number of different means, including the device design, risk analysis and management process, preclinical testing, and the clinical protocol itself, to minimize the risks to subjects and to protect their safety and welfare.

The OCS has undergone extensive preclinical and animal studies to demonstrate that the device performs as intended and all materials are biocompatible. Previous clinical studies, including the Heart EXPAND trial, have not indicated any safety signals that would preclude initiation of this study.

In addition, this clinical protocol incorporates several procedures to minimize the risks to subjects and to ensure the benefits of the clinical trial outweigh its potential risks.

- The donor heart acceptance criteria after OCS™ Heart perfusion and assessment are based on clinically relevant markers for perfusion of donor hearts on OCS™ and clinical standards of accepting conventional donor hearts for transplantation. Thus, the donor heart will be fully assessed based on the current standards of evaluating donor hearts before accepted for transplantation. The recipient should not be subjected to any surgical or medical procedures until the heart has been accepted for transplantation by the transplanting team.
- As with any heart transplant procedure, subjects will be monitored before, during and after the operative procedure. The investigators have extensive experience with heart transplants and will be trained to use the OCS™ Heart device to further minimize risk.
- The trial will be monitored to ensure the identification, documentation, and analysis of adverse events; and to ensure compliance with the protocol and procedures that are in place for conducting research to protect the safety and well-being of all subjects.

11.3. Potential Benefits

The low utilization of donor hearts has led to a severe shortage of donor hearts to meet the large and growing need for heart transplantation; the Scientific Registry For Transplant Recipients (SRTR) and Organ Procurement Transplant Network (OPTN) report that approximately 25% of the patients on the national waiting list have either died or their health deteriorated prior to a heart transplant procedure.

The OCS™ Heart System's preservation and assessment capabilities could potentially increase the rate of utilization of donor hearts that are not used due to the limitations of cold storage techniques. The previous Heart EXPAND study demonstrated an 80.6% utilization of these extended criteria donor hearts. This could improve the chances of waiting list recipients to receive a lifesaving heart transplant and reduce waiting list time and mortality. In addition, the OCS™ heart's ability to assess donor hearts after removal allows for the assessment the function of the donor heart before it is transplanted.

